# **Quality control**

**Interna**I: All research officers and Principal investigators have undergone training in all aspects of the study 10% of Records are regularly checked by principal investigator or co-investigator in each centre10 % of computer data entry will be verified by Principal investigator and co-investigator

**External**: A Data safety monitoring board is constituted. Periodic meetings of the DSMB are held regularly.

S. No	Adverse Event			Grades		
		1 (Mild)	2 (Moderate)	3 (Severe)	4 (Life Threatening)	5 (Death)
				(То	be reported as SAE)	
1	Apnea Definition: A disorder	r characterized by cessation of	• Apnea needing methyl xanthine therapy or non- invasive respirator support breathing for at least 20 seconds	Need of invasive respiratory support     or accompanied by bradycardia		• Death
2	AKI/ARF		
 
Serum creatinine increase of >=0.3 ma/dl within 48h OR
 
1.5-1.9 times the lowest previous value within & days OR
 
Urine output(ml/kg/h):<0.5 for 12h
 
	
 
Serum creatinine: 2-2.9 times the lowest previous value OR
 
Urine output (ml/kg/h):<0.5 for>=12 h
 
	
 
Serum creatinine: >=3 times the lowest previous value OR
 
>=2.5 absolute value
 
Urine output (ml/kg/h): <0.3 for >=24 h OR anuria for >=12h
 
OR need of dialysis
 
	• Death
	Definition: A disorde product homeostasis	er characterized by – Sudden	impairment in kidney function	that results in the inability to 1	naintain adequate fluid, electi	olyte, and waste
3	Arrhythmias	• Incidental detection, transient and NOT causing cardiac shock and NOT needing any therapy	• Asymptomatic but need of medical therapy	• Symptomatic causing cardiac failure and need of medical therapy	• Symptomatic needing cardio version or surgical therapy	• Death
	Definition: A disorder	r characterized by abnormal he	eart rhythm diagnosed by ECG			
4	Anaemia	Asymptomatic     anaemia NOT needing     blood transfusion		Anaemia needing blood or exchange transfusion		

S. No	Adverse Event			Grades		
		1 (Mild)	2 (Moderate)	3 (Severe)	4 (Life Threatening)	5 (Death)
				(То	be reported as SAE)	
	Definition: A disorder	r characterized by abnormal h	neart rhythm diagnosed by ECG			
5	Accidental injury	• Minor external bleeding or injury,	Need of minor surgery	
 
Fracture OR
 
Need of major surgery OR
 
Major bleeding
 
Significant intracranial bleeding
 
	Accomplished by cardiorespiratory compromise	• Death
	Definition: A disorde	r Characterized by injury to b	ody due to accident like fall or v	iolent contact with external objec	et, including accidental asphyx	ia
6	BPD	• Need of oxygen or respiratory support for at least 28 days but free of oxygen at 56 days/36 weeks PMA (mild BPD)	• Need of oxygen or respiratory support for at least 28 days but need of oxygen less than 30% at 56 days/36 weeks PMA (moderate BPD)	• Need of oxygen or respiratory support for at least 28 days but need of oxygen more than 30% or positive respiratory pressure at 56 days/36 weeks PMA (severe BPD)	
 
Severe BPD with frequent BPD spells, OR Persistent desaturations
 
Presence of cor pulmonale
 
	• Death
		r Characterized by prolonged eas of hyperinflation and coll		en therapy or respiratory support	, respiratory distress and X-ra	y picture showing
7	Cholestasis/ hepatitis		Asymptomatic cholestasis (TSB<12mg/dl)	
 
Cholestasis associated with complications like significant bleeding, encephalopathy, impairing growth OR
 
TSB 12mg/dL or more
 
	Cholestasis associated with hepatic failure	• Death

S. No	Adverse Event			Grades		
		1 (Mild)	2 (Moderate)	3 (Severe)	4 (Life Threatening)	5 (Death)
				(То	be reported as SAE)	
	Definition: A disorder bilirubin	characterized by inflammati	ion of hepatic parenchyma and/o	r biliary tract which manifests as	raised blood levels of liver en	zymes and seru
3	Extravasation injury	• Skin erythema and small swelling of extremity	

Large swelling, OR

Superficial skin necrosis

	Deep skin necrosis		
	Definition: A disorder	characterized by injury caus	ed to skin due to extravasation o	f intravenous fluid		
9	Encephalopathy		
 
Transient (lasting less than 72 h) and mild abnormality in gestation         
 
appropriate muscle tone, consciousness and reflexes, OR
 
HIE stage 1
 
 
 
	
 
Prolonged (72h or more) OR
 
Moderate to severe, OR
 
HIE stage 2 abnormalities in gestation- appropriate muscle tone, consciousness and reflexes OR
 
Presence of seizures
 
	
 
Encephalopathy causing cardiorespiratory compromise resulting in need of incubation or inotropic support, OR
 
HIE stage 3
 
	• Death
	Definition: A disorder	characterized by abnormalit	y in muscle tone, consciousness	and reflexes		
10	Gastroenteritis	Gastroenteritis without dehydration	moderate dehydration	Gastroenteritis with severe dehydration	Gastroenteritis with shock	• Death
	Definition: A disorder	characterized by inflammati	on of gastrointestinal tract manif	esting as loose motions, vomitin	g, fever and dehydration. If gas	troenteritis is a
	manifestation of sepsi	s- include it under heading or	f sepsis not under gastroenteritis	heading.		

S. No	Adverse Event			Grades					
		1 (Mild)	2 (Moderate)	3 (Severe)	4 (Life Threatening)	5 (Death)			
				(To be reported as SAE)					
11	Gangrene		Gangrene of distal     phalanx	• Gangrene extending >1 phalanx of any digit or matacarpals/metatarsals	Gangrene including long bones of limbs				
	Definition: A disorder characterized by gangrene of a part of body								
			is may only be reported as SAE. such cases, gangrene may be rep	ported as SAE.					
12	Hypoglycemia	• Blood glucose 20-40 single episode, asymptomatic, treated with oral feeds	blood glucose 20-40	• Need of intravenous glucose infusion @>12mg/kg/min or					
	Definition: A disorde	r characterized by blood gluce	ose concentration less than 40 mg	₽/dL					
13	Hyperglycemia	• NOT needing treatment with insulin	• Need of treatment with insulin	•					
	Definition: A disorde	r characterized by blood gluce	ose concentration greater than 15	0mg/dL					
14	Hypothermia	• Axillary temperature 36.0°C-36.4°C	• Axillary temperature 32.0°C-35.9°C	• Axillary temperature <32.0°C					

S. No	Adverse Event			Grades				
		1 (Mild)	2 (Moderate)	3 (Severe)	4 (Life Threatening)	5 (Death)		
				(То	be reported as SAE)			
	Definition: A disorder characterized by axillary temperature less than 36.5°C							
5	Hyperthermia	• Axillary temperature 37.6°C-38.0°C	• Axillary temperature 38.1°C-40.0°C	• Axillary temperature>40.0°C				
	Definition: A disorde	r characterized by axillary to	emperature more than 37.5°C					
16	Hypernatremia	• Serum sodium 146- 150 mEq/L	• Serum sodium 151-160 mEq/L	• Serum sodium 161-170 mEq/L	
 
Serum sodium         
 
170mEq/L OR
 
 
 
One accompanied by clinical features of seizures or altered consciousness
 
	• Death		
	Definition: A disorder characterized by increase in concentration of sodium ion in blood							
17	Hyperkalemia		• Serum potassium 5.5-6.5 mEq/L	• Serum potassium 6.5-8.0 mEa/L	• Serum potassium>8 mEq/L	• Death		
	Definition: A disorde	r characterized by increase	in concentration of sodium ion in l	blood				
18	Hyponatremia	• Serum sodium 130- 134 mEq/L	• Serum sodium 120-129 mEq/L	• Serum sodium 110-119 mEq/L	
 
Serum sodium <110 mEq/L OR
 
One accompanied by clinical features of seizures or altered consciousness
 
	• Death		

S. No	Adverse Event			Grades				
		1 (Mild)	2 (Moderate)	3 (Severe)	4 (Life Threatening)	5 (Death)		
				(To be reported as SAE)				
19	Hyperbilirubinemia	• Hyperbilirubinemia without need of therapy	• Hyperbilirubinemia needing treatment with phototherapy	• Hyperbilirubinemia needing treatment with blood exchange transfusion	• Hyperbilirubinemia with acute bilirubin encephalopathy	• Death		
	Definition: A disorder	characterized by increase in	indirect bilirubin levels in blood					
20	Neutropenia (as per Manroe or Mouzihno chart)	• Asymptomatic NOT associated with systemic infection, NOT needing any therapeutic intervention	• Asymptomatic and NOT associated with systemic infection, but needing therapeutic intervention	• Associated with systemic infection				
	Definition: A disorder characterized by decrease (below gestation and postnatal age specific threshold) in number of neutrophils in peripheral blood film.							
21	NEC		• NEC stage 1 as per Walsh Kleigmann modification of Bell's classification	• NEC stage 2 per walsh Kleigmann modification of bell's classification	• NEC stage 3 as per Walsh Kleigmann modification of Bell's classification	• Death		
	Definition: A disorder characterized by inflammation of gut which may progress to intestinal necrosis							
			Causing fracture or					

S. No	Adverse Event	Grades						
		1 (Mild)	2 (Moderate)	3 (Severe)	4 (Life Threatening)	5 (Death)		
				(То	be reported as SAE)	 		
23	Pressure sore		• Small (<2cm)- healing happens in <1 week	• Major pressure sore (>2cm) and requiring surgical intervention or non-healing pressure sore				
	Definition: A disorde	r characterized by formation o	f ulcers over pressure sites					
24	Polycythemia	Asymptomatic NOT needing treatment	• Symptomatic needing treatment with fluid relaxation or partial	• Associated with complication such as NEC, thrombosis				
			exchange transfusion					
	Definition: A disorde gestation norms.	r characterized by increased h		ne with haematocrit value 65% c	r more in blood as per gestatio	n and postnatal		
25		er characterized by increased h		
 
Free fluid in the pleural cavity requiring significant increase in respiratory support or requiring ICD drainage
 
	
 
r more in blood as per gestation
 
Fluid in pleural cavity resulting in circulatory collapse
 
	and postnatal     Death		
25	gestation norms. Pleural effusion	er characterized by increased ha	
 
Minimal fluid in the pleural cavity requiring no/minimal change in respiratory support
 
	• Free fluid in the pleural cavity requiring significant increase in respiratory support or	• Fluid in pleural cavity resulting in circulatory	-		

S. No	Adverse Event			Grades			
		1 (Mild)	2 (Moderate)	3 (Severe)	4 (Life Threatening)	5 (Death)	
				(То	be reported as SAE)		
27	PDA	Asymptomatic PDA	• PDA needing medical treatment	• PDA needing surgical treatment or resulting in cardiac failure	• PDA causing life threatening complications such as AKI, severe pulmonary haemorrhage NEC stage 3	• Death	
	Definition: A disorder	r characterized by persistent n	on-closure of ductus arteriosus				
28	PVL	Periventricular flare     without cyst formation	• Periventricular leukomalacia with cysts formation in frontal, parietal regions	Periventricular leucomalacia with cysts formation in occipital periventricular white matter			
	Definition: A disorder characterized by hypoxic-ischemic injury to periventricular brain resulting in disability						
29	Periventricular – intraventricular haemorrhage (P/IVH)	• Grade 1 IVH	Grade 2 IVH	
 
Grade 3 IVH, OR
 
PVHI, OR
 
Any grade IVH manifesting as seizure or post haemorrhagic hydrocephalus
 
	
 
Post – haemorrhagic hydrocephalus needing shunt placement, OR
 
IVH causing significant respiratory compromise requiring ventilation or hemodynamic compromise requiring vasopressors
 
	• Death	

S. No	Adverse Event			Grades				
		1 (Mild)	2 (Moderate)	3 (Severe)	4 (Life Threatening)	5 (Death)		
			(То	be reported as SAE)				
30	Pulmonary hemorrage	• Occasional small bleed occurring spontaneously or during endotracheal suction requiring no/minimal change in respiratory support	• Recurrent small bleeds, does not require a transfusion/significant hike in respiratory support.	
 
Need for blood/component transfusion, OR
 
Need for significant augmentation of respiratory support, OR
 
Prolongation of ventilation
 
	Shock requiring vasopressors	• Death		
	Definition: A disorder characterized by bleeding from the bronchial wall and / or lung parenchyma manifested as endotracheal bleeding or bleeding from mouth in a non- intubated baby.							
31	ROP	• Any ROP which is less severe than type  / 2 (this does not refer to stage 1 or 2) ROP.	• Type 2 ROP as described in ETROP study	• Type 1 ROP as described in ETROP study or ROP needing treatment				
	Definition: A disorder characterized by abnormal fibro vascular proliferation in retina         Type 1 ROP – any of 3: (1) Zone I, any stage ROP with plus disease, (2) Zone I, stage 3 ROP without plus disease, or (3) Zone II, stage 2 or 3 ROP with plus disease         Type 2 ROP – any of two : (1) Zone I, stage 1 or 2 ROP without plus disease, (2) Zone II, stage 3 ROP without plus disease							

S. No	Adverse Event	Grades						
		1 (Mild)	2 (Moderate)	3 (Severe)	4 (Life Threatening)	5 (Death)		
				(То	be reported as SAE)	 		
32	Seizures		
 
Single episode of seizures without cardiorespiratory compromise due to transient metabolic abnormalities like hypoglycaemia, hypocalcaemia
 
	
 
Multiple episodes of seizures OR
 
Seizures needing treatment with antiepileptic drug
 
	
 
Status epilepticus OR
 
Seizures causing cardiorespiratory compromise
 
	• Death		
	Definition: A disorder of	characterized by abnormal in	voluntary movements of muscl	es				
33	Spontaneous Intestinal Perforation (SIP)			
 
SIP NOT needing surgical management by laparotomy and NOT
 
causing cardiorespiratory compromise
 
	
 
SIP needing surgical management by laparotomy or leading
 
to cardiorespiratory compromise
 
	• Death		
	Definition: A disorder of	characterized by perforation	of intestine without any clinical	or intraoperative or pathological	evidence of NEC			
34	Shock		• Hypotension or decreased organ perfusion lasting for <6 hours needing volume expander and resolving without consequence	• Hypotension or decreased organ perfusion needing /vasopressor(s)/ ionotropes	Catecholamine resistant shock	• Death		

S. No	Adverse Event			Grades		
		1 (Mild)	2 (Moderate)	3 (Severe)	4 (Life Threatening)	5 (Death)
				(To be reported as SAE)		
35	Sepsis (irrespective of etiology-bacterial, viral,fungal,protozoa l) includes pneumonia, meningitis or bone- joint infection	characterized by the presence	
 
Culture negative sepsis, OR
 
Ventilator associated pneumonia requiring no/ minimal increase in respiratory support
 
	
 
Culture positive sepsis OR
 
Meningitis OR
 
Encephalitis, OR
 
Presence of sclerema, OR
 
Ventilator associated pneumonia requiring
 
significant increase in respiratory support
 
	
 
Septic shock requiring vasopressors, OR
 
Multi – organ dysfunction such as presence of AKI, DIC-bleeding, OR
 
Ventilator associated pneumonia resulting in
 
persistent desaturations despite high level ventilator support
 
	• Death
	lead to shock and / or	• •		in the blood stream that cause a r	apary progressing systemic rea	letton that may
36	Thromboembolism	• Asymptomatic , NOT needing treatment	Causing gangrene of distal phalanx	• Causing gangrene extending > 1 phalanx of any digit or metacarpals/metatarsals	• Causing gangrene including long bones of limbs or any internal organ like brain, kidney or lungs	
	Definition: A disorder	characterized by thromboem	polic phenomenon involving a v	ascular system	,  	
37	Thrombocytopenia	• NOT associated with bleeding and above the threshold for platelet transfusion	• NOT associated with active bleeding but needing platelet tranfusion	• Associated with bleeding or platelet count less than 20,000.		• Death

S. No	Adverse Event			Grades					
		1 (Mild)	2 (Moderate)	3 (Severe)	4 (Life Threatening)	5 (Death)			
				(To be reported as SAE)					
	Definition: A disorder characterized by decrease in number of platelets (less than 150,000/µL in peripheral blood								
38	Liver dysfunction	Asymptomatic raised liver -		Symptomatic liver	Decompensated liver	Death			
		liver enzymes, treatment		dysfunction	function (e.g., ascites,				
		not indicated			coagulopathy,				
					encephalopathy, coma)				
	Definition: A disorder characterized by a pathologic process involving liver parenchyma								
39	Anaphylaxis			Symptomatic bronchospasm,	Life-threatening	Death			
				with or without urticaria;	consequences; urgent				
				parenteral intervention	intervention indicated				
				indicated; allergy-related					
				edema/angioedema;					
				hypotension					
	Definition: A disorde	r characterized by an acute inflam	matory reaction resulting	from the release of histamine and h	l histamine-like substances from	n mast cells.			
		ivity immune response.	initiation y reaction resulting						
	causing a nypersonsit	in the response.							

S. No	Adverse Event	Grades					
		1 (Mild)	2 (Moderate)	3 (Severe)	4 (Life Threatening)	5 (Death)	
				(To be reported as SAE)			
40	Hemolysis	Laboratory evidence of hemolysis only (e.g., direct antiglobulin test; DAT; Coombs'; schistocytes; decreased haptoglobin) ized by laboratory test results that indicate RBC destruction	Evidence of hemolysis and >=2 gm decrease in hemoglobin	Transfusion or medical intervention indicated (e.g., steroids)	Life-threatening consequences; urgent intervention indicated	Death	
41 42	Definition: Disorder Deranged coagulogram	characterized by widespread de INR or APTT >1 - 1.5 x ULN; INR >1 - 1.5 times above baseline if on	estruction of platelets INR or APTT >1.5 - 2.5 x ULN; INR >1.5 - 2.5 times above baseline if on anticoagulation	INR or APTT >2.5 x ULN; INR >2.5 times above baseline if on anticoagulation	-	-	
	Disseminated intravascular coagulation	anticoagulation based on laboratory test result - r characterised by systemic pat	Lab findings of DIC with no bleeding	ratio of the patient's prothrombin Laboratory findings and bleeding	Life-threatening consequences; urgent intervention indicated	Death	

S. No	Adverse Event	Grades						
		1 (Mild)	2 (Moderate)	3 (Severe)	4 (Life Threatening)	5 (Death)		
				(То	be reported as SAE)	·		
43	Arthritis	Mild pain associated with	Moderate pain or joint	Severe pain associated with	-	-		
		erythema, inflammation	swelling, limitation of	signs of inflammation,				
			movement	erythema or joint swelling;				
				irreversible joint damage;				
				disabling				
	Definition: a disorder characterised by inflammation involving a joint							
44	Rash	Macules/ papules/ pustules	Macules/ papules/ pustules	Macules/ papules/ pustules	-	-		
		covering <10% body	covering 10% - 30% body	covering >30% body surface				
		surface area with or	surface area with or without	area with or without				
		without symptoms	symptoms	symptoms				
	Definition: a skin dise	order characterised by the pres	ence of macules or papules are p	pustules	 			
45	Superficial	-	Present	-	-	-		
	thrombophlebitis							
	Definition: a disorder characterised by a blood clot in inflammation involving a superficial vein of the extremities							
46	Urticaria	Urticarial lesions covering	Urticarial lesions covering 10	Urticarial lesions covering				
		<10% BSA; topical	30% BSA; oral intervention	>30% BSA; IV intervention				
		intervention indicated	indicated	indicated				
	Definition: A disorda	r characterized by an iteby ski	 n gruption characterized by where	 le with pale interiors and wall de	afined red margins			
	Definition: A disorder characterized by an itchy skin eruption characterized by wheals with pale interiors and well-defined red margins							

S. No	Adverse Event	Grades					
		1 (Mild)	2 (Moderate)	3 (Severe)	4 (Life Threatening)	5 (Death)	
				(To be reported as SAE)			
47	Diarrhea	Increase of <4 stools per	Increase of 4 - 6 stools per	Increase of $\geq$ =7 stools per	Life-threatening	Death	
		day over baseline	day over baseline	day over baseline;	consequences; urgent		
				incontinence; hospitalization	intervention indicated		
				indicated			
	Definition: a disorder	r characterized by frequent wa					
48	Vomiting	1 - 2 episodes (separated	3 - 5 episodes (separated by 5	>=6 episodes (separated by 5	Life-threatening	Death	
		by 5 minutes) in 24 hrs	minutes) in 24 hrs	minutes) in 24 hrs; tube	consequences; urgent		
		•		feeding, TPN or	intervention indicated		
				hospitalization indicated			
	Definition: A disorde	er characterized by the reflexiv		•			

Version dated 15 October 2018

Title:

Comparison of the Efficacy of a 7-day Versus 14-day Course of Intravenous Antibiotics in the Treatment of Uncomplicated Neonatal Bacterial Sepsis: a Randomized Controlled Noninferiority Trial

NCT number: NCT 03280147

Date of document: 26 September 2019

STATISTICAL ANALYSIS PLAN

The baseline variables shall be described using descriptive statistics. Categorical variables will be described by percentages. Numerical variables will be described as mean (standard deviation) or median (1st, 3rd quartile), depending on distribution. Normality of distribution of numerical variables will be tested by Shapiro Wilk test and QQ plot.

The primary outcome variable is "definite or probable relapse" within 21 days after stopping antibiotics. Secondary outcome variables include individually definite and probable relapse within 21 days and 28 days after stopping antibiotics; definite and probable relapse within 28 days and 35 days after randomization; "definite or probable relapse" within 28 days and 35 days after randomization; secondary bacterial infections within 35 days after randomization and adverse events within 35 days after randomization. Analysis will be both per protocol as well as intention-to-treat, as this is a noninferiority trial.

As all the outcome variables are categorical, chi-square test with Yates correction or Fisher's Exact test, as applicable, will be used to compare the 2 groups.

Sub-group analysis has been planned for the following sub-groups: birth weight 1000-1499 grams, 1500 to 2000 grams, and >2000 grams, those infected with gram positive organisms versus the rest and those with radiological pneumonia versus those without radiological pneumonia. A p-value for the test of interaction (Breslow-Day test) will be derived for the subgroup analyses.

Multi variable logistic regression analysis will be performed to determine the relationship between group membership (7-day course of antibiotics versus 14-day course of antibiotics) and the primary outcome after adjusting for the following baseline covariates: birth weight, age of neonate, infection with gram positive organisms, number of days by which clinical remission of sepsis achieved prior to randomization.

Mid-term analyses will be performed by an independent Data Safety Monitoring Board at 1/3rd and 2/3rd of expected recruitment.

Data Safety Monitoring Board will monitor serious adverse events in the trial. O'Brien-Fleming's stopping criteria will be used for the primary outcome while Pocock's stopping rules will be used for serious adverse events.

Analysis shall be done using the statistical software packages SPSS version 22.

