# Not eligible for randomization

- Sterile blood culture
- Suspected contaminants in blood culture.
- Growth of Staphylococcus aureus in blood culture
- Growth of fungal organism in blood culture
- Diagnosis of meningitis, septic arthritis, osteomyelitis, abscess
- Has not gone into remission on day 5 or have recurrence of symptoms from day 5 through day 7
- If the empiric antibiotic is resistant but neonate has shown improvement of signs and symptoms of sepsis and there is ambiguity regarding in vivo sensitivity of antibiotic use

These elaborate criteria have been drawn up because this is an equivalence (non-inferiority) trial. In an equivalence trial, extra care has to be taken to exclude subjects who are likely to respond irrespective of which treatment arm they are in and also subjects who are not likely to respond irrespective of which treatment arm they are in. This is because inclusion of such patients would bias the results towards no effect (ie equivalence).

Data from enrolment until the point of determining eligibility for randomization will be recorded in the "Enrolment sub-form" of Proforma A of the case report form.

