### Secondary outcomes

"Definite relapse" and "probable relapse" will be separate secondary outcomes, each assessed at 21 days and 28 days after antibiotic completion. [This was originally "definite or probable relapse"].

Episodes of relapses (# 1-4) will be analyzed both as per protocol and as per intention-to-treat:

1. "Definite relapse": by 21 days after antibiotic completion.

2. "Probable relapse": by 21 days after antibiotic completion.

3. "Definite relapse": by 28 days after antibiotic completion.

4. "Probable relapse": by 28 days after antibiotic completion.

Episodes of relapses (# 5-7) will be analyzed as per intention-to-treat:

5. "Definite or probable relapse" in the 28-day period after randomization and 35-day period after randomization

6. "Definite" in the 28-day period after randomization and 35-day period after randomization

7. "Probable" in the 28-day period after randomization and 35-day period after randomization]

The following will also be analysed in the 35-day period of observation after randomization:

(A) Episodes of secondary infections during the observation period. These may be bacterial or fungal.

(B) Adverse events: All fresh adverse events occurring after randomisation would be recorded. Adverse events with onset prior to randomisation would be recorded only if there is worsening after randomisation. Adverse events are listed and defined as per Appendix 5.

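### The SAP restricts the secondary-infection outcome to bacterial infections where the protocol counts bacterial and fungal, so a literal reading drops fungal episodes from that comparison

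*SAP*

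**What the plan says.** The protocol, under Secondary outcomes, introduces a pair of outcomes with "The following will also be analysed in the 35-day period of observation after randomization". The first of the pair, labelled (A), is "Episodes of secondary infections during the observation period. These may be bacterial or fungal". The second, (B), is adverse events, defined in the protocol's graded adverse event table.

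The SAP's list of secondary outcomes ends with "secondary bacterial infections within 35 days after randomization", followed by adverse events over the same window. These are the counterparts of (A) and (B). The word fungal does not appear anywhere in the SAP. For all outcomes, the SAP then states that a "chi-square test with Yates correction or Fisher's Exact test, as applicable, will be used to compare the 2 groups".

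Two other places in the protocol bear on the point. Item 35 of the adverse event table reads "Sepsis (irrespective of etiology-bacterial, viral,fungal,protozoa l) includes pneumonia, meningitis or bone- joint infection". The list of reasons not to randomize includes "Growth of fungal organism in blood culture".

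**The concern.** Two definitions of one secondary outcome are in force, and neither document says that it replaces the other. The SAP is dated 26 September 2019. The protocol carries the same date in a footer in its mid-term analysis section, and 15 October 2018 at the end of the adverse event table. The dates therefore do not settle which text governs.

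The difference changes what is counted. Under the protocol, a neonate whose only new infection after randomization is fungal has had the outcome. Under the SAP's wording the same neonate has not.

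The trial compares 7 with 14 days of antibiotics. It is plausible that a longer course affects later fungal infection, in which case the excluded events could bear on the value of a shorter course. That rationale is mine; the protocol gives no reason for including outcome (A). What the protocol does settle is that fungal episodes belong in it.

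**Working it through.** **1. The two definitions side by side.**

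| | Protocol, outcome (A) | SAP |
|---|---|---|
| Event | secondary infections | secondary bacterial infections |
| Fungal episodes | included by name | not mentioned |
| Window | 35 days from randomization | 35 days from randomization |
| Reason for narrower scope | – | none given |

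Only the scope differs.

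**2. Could a fungal episode be counted in another infection outcome?** Under Primary outcome variables, definite relapse needs the organism of the original episode with a similar antibiogram. Probable relapse needs a clinical diagnosis of bacterial sepsis with a sterile blood culture. Fungal growth in the index culture bars randomization, so a later culture that grows a fungus shows a new organism and is not sterile. It meets neither definition. Among the infection outcomes, (A) is the only place for it.

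**3. Does the exclusion before randomization explain the SAP's wording?** No. It concerns the culture that brought the infant into the study, not infections arising afterwards.

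**4. Does the adverse event analysis cover it?** In part. Item 35 counts sepsis of any cause, and the SAP analyses adverse events over the same 35 days. But the item pools fungal sepsis with bacterial sepsis, so a definite relapse, being culture-positive sepsis, falls in the same item. If relapse were commoner in one arm and fungal infection in the other, the two could offset each other within it. The SAP also does not say whether adverse events are compared item by item or overall.

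**5. Size.** Neither document gives a rate of secondary infection or a fungal share, so the following rests on assumptions. Take 6% secondary infection in one arm and a fungal share of 10% to 50%.

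- All 350 randomized: 350 × 0.06 = 21 events. Fungal: 21 × 0.10 = 2.1; 21 × 1/3 = 7; 21 × 0.50 = 10.5.
- Allowing for the 10% loss to follow-up in the sample size section: 350 × 0.90 = 315; 315 × 0.06 = 18.9 events. Fungal: 18.9 × 0.10 = 1.9; 18.9 × 1/3 = 6.3; 18.9 × 0.50 = 9.5.

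Under these assumptions about 2 to 10 events per arm would move from event to non-event.

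**6. Does the design figure depend on this?** The protocol's inputs are a 10% event rate, a 7% margin, one-sided alpha of 5%, power of 90% and about 10% loss.

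- n per arm = (z₀.₉₅ + z₀.₉₀)² × 2 × p(1 − p) / margin² = (1.645 + 1.282)² × 2 × 0.10 × 0.90 / 0.07² ≈ 314.6, rounded up to 315.
- Allowing for loss: 315 / 0.90 = 350, which matches the stated 350 per arm.

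The secondary-infection outcome does not enter this calculation, so correcting its wording leaves the sample size unchanged.

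**The case against.** The best case on the other side has four parts.

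- **Fungal sepsis is still compared between arms.** This stands: item 35 and the SAP's 35-day adverse event analysis keep it in view. A reader might infer from the SAP's wording that fungal infections disappear from the trial, and the documents do not support that. What is lost is their place in the named secondary-infection comparison, which a pooled sepsis item cannot restore.
- **The SAP's list is not stated to be complete.** It says that the secondary outcomes *include* the listed items, and the narrower wording may well be a drafting slip. That is a fair account of the cause, but not a cure. This item is listed, with the qualifier bacterial attached, and whoever codes it has to choose.
- **Nothing suggests a choice made after seeing data.** This stands. A reader might infer that the two definitions exist so that one can be picked later. The documents show no sign of that, and a bacterial-only report could be checked against the protocol. The reason to align the texts is that they conflict.
- **The size is not known, and no hidden difference has been shown.** This stands too. The 6% rate and the fungal shares are assumptions. They describe one arm, and they do not show that any difference between arms would be masked.

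**Conclusion.** The inconsistency is real and narrow. Followed literally, the SAP removes fungal episodes from a secondary outcome that the protocol defines to include them, and no other infection outcome takes them up. Adverse event item 35 is partial cover only.

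The number of events affected cannot be derived from the documents. The range of about 2 to 10 per arm holds only for an assumed 6% secondary-infection rate and a fungal share between 10% and 50%; the conclusion rests on the wording and not on these figures. The primary outcome, the non-inferiority margin, the sample size and the stopping rules are untouched. This is a correction that should be made to a secondary outcome definition, not a threat to the trial's main conclusion.

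**What to change.** In the SAP's list of secondary outcomes, replace *secondary bacterial infections* with *secondary infections (bacterial or fungal)* and leave the 35-day window as it is. If the narrower scope was intended, the SAP should say so and give the reason, and the protocol should be brought into line. A breakdown by type within each arm would be useful but is optional, since the protocol does not ask for it.

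The cost is one phrase. The protocol already has staff record every episode of illness through day 35, with the laboratory details obtained, so no new data collection is called for and the sample size stays at 350 per arm.
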